7.3 LOST TO FOLLOW-UP

A participant will be considered lost to follow-up if they complete at least one study visit and subsequently miss two consecutive study visits and are unresponsive to study contact (after at least 3 attempts).

If a participant misses a scheduled study visit:

- The OT or study coordinator will attempt to contact the participant, reschedule the missed visit, counsel the participant on the importance of maintaining the assigned visit schedule and ascertain if the participant wishes to and/or should continue in the study.
- Before a participant is deemed lost to follow-up, the investigator or designee will make every effort to regain contact with the participant. These contact attempts will be documented in the Master File.
- Should the participant continue to be unreachable, he or she will be considered to have withdrawn from the study with a primary reason of lost to follow-up.

8 STUDY ASSESSMENTS AND PROCEDURES

8.1 ENDPOINT AND OTHER NON-SAFETY ASSESSMENTS

A trained tester blind to treatment group will conduct Pre and Post testing while participants are on their regular medication (to prevent motor interference⁶³ and best represent their function in daily life). Testing will occur at the same time of day to control for potential effects of dosage timing or wearing off. Follow-up assessment will occur via web-based or mailed survey.

Primary outcomes:

Aim 2

- Therapist fidelity: Trained raters who are blind to study purpose and treatment group will use the *MC Fidelity Tool* to perform the following ratings. *Adherence*: Proportion of protocol steps that occurred within the session will be rated as present or absent. *Proficiency*: Quality of delivery of each of MC's critical treatment components will be rated on a 4-point scale (0=Did not occur, 1=Little Evidence/Inadequate, 2=Emerging/Adequate, 3=Proficient; averaged for a competence score) with detailed guidelines for each component and anchor. The raters will rate a random sample (30%, n = 180) of MC and Control session audiofiles (evenly distributed across condition, OT, treatment session number, and study month).
- Acceptance: We will administer the *Client Satisfaction Questionnaire* (CSQ-8)^{76,77} at post-treatment via mailed or web-based survey. Items have 4-point response scales (3-4: positive, 2: neutral, 1: negative) and are summed for a total score; higher scores indicate higher acceptance.
- Receipt: The raters will rate participants' engagement in treatment sessions with the *Pittsburgh Rehabilitation Participation Scale* (PRPS)⁷⁸ from the audiofiles (3 sessions per participant). The PRPS is a 6-point scale (1=None, 6=Excellent) with full descriptions of each anchor. Session scores are averaged for a single score, which is reliable and predictive of rehabilitation outcomes^{78,79}.
- Enactment (i.e. Adherence): The raters will code homework completion for each session (0=Did not do, 0.5=Partial, 1=Complete). We will sum these scores and divide by the total number of homework assignments (10) to yield a homework completion rate for each participant.

Aim 3

- **Functional cognition:** The *Bangor Goal-Setting Interview (BGSI)*^{80,81} offers a standardized means of eliciting individual goals and rating goal attainment over time and has been successfully used in cognitive rehabilitation RCTs with older adults, including those with mild to moderate dementia⁸¹⁻⁸³. During the first intervention session, the OT will conduct a semi-structured interview to gain an understanding the participant's functional cognitive performance and potential problem areas and goals. Part of the participant's first homework assignment will be to think further about problem areas and functional cognitive goals, and they will be provided with a handout and Activity Checklist to guide and document the process. At the second session, the OT and participant will review what was discussed in the first session and anything the participant wishes to add or modify. Then they will identify and set goals for 3-5 real-life functional cognitive problems. They and their informants will rate each of their goals for Attainment, Importance, and Readiness to Change on 10-point scales (e.g., Attainment: 1=Cannot do or am not doing successfully, 10=Can do and am doing very successfully) in the second session (Pre) and then again at Post and Follow-up. Goal attainment ratings are averaged to yield mean attainment scores⁸¹.

Additional Measures:

In addition to the primary measures above, we will collect other data to characterize participants, as covariates, or as exploratory/secondary outcome measures of treatment effect (see Table below). Some objective and informant-report measures of functional cognition will be administered as exploratory outcomes in this trial to assess their potential to be co-primary outcomes for the future RCT, thus mitigating potential limitations associated with self-report. The rater will retrieve clinical characteristics from electronic medical records and confirm with the participant in the Pre assessment.

Purpose/Domain	Measure/Description
Baseline characteristics:	
Demographics	e.g., age, sex, education, ethnicity/race, living/work status, comorbidities
Clinical characteristics	e.g., disease duration, side/type of onset, medications, Hoehn & Yahr stage
Motor dysfunction	Unified Parkinson Disease Rating Scale (UPDRS) Parts II & III
Non-motor dysfunction	Beck Depression Inventory-II; Parkinson Anxiety Scale; Apathy Scale; Fatigue Severity Scale
Cognition	Montreal Cognitive Assessment (MoCA), NIH Toolbox Cognitive Battery
Exploratory/secondary outcomes:	
Functional cognition (proximal)	Objective performance: Weekly Calendar Planning Activity ⁸⁴
Functional cognition (proximal)	Patient-reported: NeuroQOL Cognitive Function; PD-Cognitive Functional Rating Scale (PD-CFRS) ⁸⁵ (self & informant); Global Rating of Change ⁸⁶ ; SRSI
Self-efficacy (proximal)	Patient-reported: Cognitive Self-efficacy Scale; General Self-efficacy Scale ⁸⁷
Participation (distal)	Patient-reported: NeuroQOL Ability to Participate in Social
Process measure:	Credibility and Expectancy Questionnaire ⁸⁸

See also Sections 1.3, 3

8.2 SAFETY ASSESSMENTS

See the Data & Safety Monitoring Plan.

8.3 ADVERSE EVENTS AND SERIOUS ADVERSE EVENTS

See the Data & Safety Monitoring Plan.

8.4 UNANTICIPATED PROBLEMS

See the Data & Safety Monitoring Plan.

9 STATISTICAL CONSIDERATIONS

9.1 STATISTICAL HYPOTHESES

Aim 1: Examine the feasibility of the MC approach within an RCT.

- H1: Study recruitment will be 4 participants/month, retention in both treatment groups will be $\geq 85\%$, and $\geq 85\%$ of participants in both groups will complete the intervention in 12 weeks.

Aim 2: Demonstrate adequate treatment fidelity to the MC approach.

- H2a: Therapists will deliver MC with good adherence ($\geq 80\%$) and proficiency (scores $\geq 2/3$, indicating Adequate).
- H2b: MC participants will have good acceptance (CSQ-8 $\geq 24/32$, indicating all positive responses), receipt (PRPS $\geq 4/6$, indicating at least “Good”) and enactment (homework completion $\geq 80\%$).

Aim 3: Obtain preliminary estimates of the MC approach’s effect on patient-reported functional cognition.

- H3 (exploratory): MC participants will report greater improvement in functional cognition than Control participants immediately and 3 months after treatment.

9.2 SAMPLE SIZE DETERMINATION

We will enroll 30 participants per group ($N = 60$). Although not required for an R21 proposal, we provide power analyses for our feasibility and fidelity hypotheses (Aims 1 & 2) assuming 15% attrition (see Table). We also estimate power for our (exploratory) pre-post comparisons of treatment effect (Aim 3). Based on our preliminary data (Goal Attainment $\Delta M = 2.4$, $SD = 0.97$), with $n = 30$ per group we will be able to detect mean differences in change of 0.85 in Attainment (2-tailed, $\alpha = 0.05$, 90% power). However, we want to reiterate that our reason for measuring treatment effect in this study is not to demonstrate efficacy but to obtain effect size estimates to power an efficacy trial. Our proposed sample size will provide enough information to achieve our aims and is feasible to accomplish in the timeframe of an R21.

Confidence bounds around target thresholds assuming 15% attrition (for Aim 2) and 95% confidence level.		
Aim	Outcome (with preliminary data source reference)	Target (Lower, upper)
1	Recruitment and retention	85% (73 – 93)
2a	Adherence (n=153 observations) ⁶¹	80% (78 - 82)

2a	Proficiency (n=153 observations) ⁶¹	3 (2.9 – 3.1)
2b	Acceptance: CSQ ⁵³	24 (23.8 – 24.2)
2b	Receipt: PRPS ⁷⁸	4 (3.8 – 4.2)
2b	Enactment: Homework completion ⁵³	80% (75 – 85)

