9.3 POPULATIONS FOR ANALYSES

Our primary population for analysis of treatment effect (Aim 3) will be the Intention-to-Treat (ITT) Analysis Population (i.e., all randomized participants). We will also conduct Per-Protocol analyses on the subset considered to have completed the intervention (at least 4 treatment sessions).

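### Section 9.2 claims 90% power for a 0.85-point Attainment difference on the full 30 enrolled per group; at the plan's own 85% retention, power is about 86–87%

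*Combined protocol and SAP*

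**What the plan says.** Section 9.2 plans 30 participants per group, 60 in all. From preliminary data it takes a mean change in Goal Attainment of 2.4 with SD 0.97. It then states that at 30 per group "we will be able to detect mean differences in change of 0.85 in Attainment", under the settings "2-tailed, $\alpha = 0.05$, 90% power". This is the only power statement for Aim 3.

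Attrition appears in the same paragraph, but for other aims. The section offers "power analyses for our feasibility and fidelity hypotheses (Aims 1 & 2) assuming 15% attrition", and the table below it is headed "Confidence bounds around target thresholds assuming 15% attrition (for Aim 2) and 95% confidence level". The Aim 3 sentence carries no attrition figure.

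Three other places bear on how many participants will supply data:
- Sections 9.1 and 9.4 set a retention hypothesis of at least 85% in both groups. Section 9.4 reports 87.5% retention in the preliminary study.
- Section 7.2 says that participants who leave the study are not replaced.
- Section 9.3 states: "Our primary population for analysis of treatment effect (Aim 3) will be the Intention-to-Treat (ITT) Analysis Population".

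**The concern.** A detectable difference should be computed on the participants expected to have the outcome. Here the enrolled number is used, while the plan elsewhere expects to lose about 15% and does not top up. If the Aim 3 comparison loses participants at that rate, the stated 90% power for 0.85 points is not reached.

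There is also a question of unit. The sentence reads as a difference on the Attainment scale, but a two-sample t calculation on the stated inputs does not return exactly 0.85 points. It returns 0.85 in SD units. A reader cannot tell which unit or which method lies behind the number.

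The stakes are modest. The sentence tells readers how precise the pilot's effect estimate will be, and that estimate is meant to inform the sample size of the definitive trial.

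**Working it through.** **Inputs (all Section 9.2).** 30 per group, equal groups; two-sided alpha 0.05; power 90%; SD of change 0.97; stated detectable difference 0.85. Attrition of 15% is the section's figure for Aims 1 and 2, applied here to Aim 3 as an assumption: 30 × 0.85 = 25.5 per group, that is 25–26.

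**Method.** Two-sample t-test on change, n per group, degrees of freedom 2n − 2. For a true difference δ the noncentrality is λ = (δ / SD) × √(n / 2). Power is the probability that a noncentral t variable with this λ exceeds the two-sided 5% critical value. The detectable standardised effect d is the value of δ / SD at which power is 90%; in points it is d × 0.97.

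**The plan's own figure, at n = 30.**
- For δ = 0.85 points: 0.85 / 0.97 = 0.876, and λ = 0.876 × √15 = 3.394. Power is 91.6%, so the claim of 90% is met.
- Solved for 90% power: d = 0.851, and 0.851 × 0.97 = 0.826 points. (The normal approximation gives 0.812 points.)
- So 0.85 read as points is conservative by about 0.85 − 0.826 = 0.024.

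**The same calculation with fewer evaluable participants.**

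| Evaluable per group | λ for 0.85 points | Power for 0.85 points | Detectable d, 90% power | Detectable points, 90% power |
|---|---|---|---|---|
| 30 | 3.394 | 91.6% | 0.851 | 0.826 |
| 29 | 3.337 | 90.6% | 0.866 | 0.840 |
| 28 | 3.279 | 89.6% | 0.882 | 0.856 |
| 27 | 3.220 | 88.5% | 0.899 | 0.872 |
| 26 | 3.160 | 87.3% | 0.917 | 0.889 |
| 25.5 | 3.129 | 86.6% | 0.926 | 0.898 |
| 25 | 3.098 | 85.9% | 0.936 | 0.908 |

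Ninety percent power for 0.85 points needs 29 evaluable per group, so the claim survives the loss of one person per arm. Loss of 15% is 30 − 25.5 = 4.5 per arm.

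**Unit.** At n = 30 the t-test gives d = 0.851, which rounds to the printed 0.85. But 0.85 points can be reached in another way: a rank test with efficiency 0.955 has an effective n of 30 × 0.955 = 28.65 and a detectable difference of 0.846 points.

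**The case against.** **The sentence is true as printed.** It says 30 per group, and at 30 per group power for 0.85 points is 91.6%. This stands. The point concerns what happens after loss, not the arithmetic at full enrolment.

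**The 15% is not stated for Aim 3.** This also stands. The paragraph ties it to Aims 1 and 2, and the table heading to Aim 2. The value of 0.90 points is therefore what follows if the plan's retention expectation is carried over to Aim 3; the section does not claim it. Carrying it over is reasonable, because the same 60 people supply all three aims.

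**Intention-to-treat and the mixed model keep everyone in.** This stands in part. Under Section 7.1, a person who stops treatment but stays in the study still has the post-treatment assessment. Retention as defined in Section 4.4 runs to the 3-month follow-up, so loss by the post-treatment visit may be below 15%. The rows for 26 to 29 cover that case. But a model recovers little of a pre-post change whose post-treatment score was never observed. Moreover, Section 8.1 takes the baseline Attainment rating in the second treatment session, after randomisation, so someone who leaves before then has no baseline score either.

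**A reader might infer that 0.85 is a standardised effect printed as points.** The match with 0.851 invites that reading. The documents do not support it as a finding: nothing calls the figure standardised, it holds as points at 30 per group, and a rank-test calculation or conservative rounding would also give it. If it were a mislabel, it would be worth about 0.02 points, on the safe side.

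**A reader might also want a range reflecting the uncertainty of the preliminary SD.** Section 9.2 does not give the number of participants behind the 0.97, so any such range would rest on a guess.

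**Conclusion.** The point holds as a missing attrition allowance of low severity. At 25–26 evaluable per group, power for a 0.85-point difference is about 86–87% rather than 90%, and the difference detectable at 90% power is about 0.90 points (0.89–0.91). This assumes SD 0.97, equal groups, a t-test on pre-post change, and 15% loss of evaluable participants from each arm. With smaller loss the shortfall shrinks, and it disappears at 29 or more per group.

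The unit of 0.85 should be made explicit, but no error of unit is established.

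Severity is low for three reasons. Aim 3 is labelled exploratory. Sections 9.2 and 9.4 both say that the purpose is estimation and not proof of efficacy. The Aim 3 failure criterion in Section 3 uses an average change of 1 point or less together with a confidence bound, and does not use 0.85.

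**What to change.** Replace the Aim 3 power sentence in Section 9.2 with wording such as: *With 25–26 evaluable participants per group after 15% attrition and SD 0.97, the study has 90% power (two-sided alpha 0.05) for a difference in change of about 0.90 Attainment points (standardised effect 0.92–0.94); with no attrition the figure is 0.83 points.* If a method other than a two-sample t-test lies behind the 0.85, name it.

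The cost is one sentence and a slightly less favourable figure. Sample size, analysis and decision criteria are unchanged.

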To obtain preliminary estimates of effect on self-efficacy.	Cognitive Self-efficacy Scale, General Self-efficacy Scale	
Tertiary/Exploratory		
To obtain preliminary estimates of effect on participation.	NeuroQOL Ability to Participate in Social Roles and Activities	

The following criteria will be used to declare failure:

Aim 1: Feasibility

- ≤ 60% retention in the study intervention

- $\leq 75\%$ retention in the study (80-85% is typically considered good in behavioral trials; e.g., Abshire et al., 2017; Coday et al., 2005)
- Note: Participants excluded post-Randomization count as failures in the above retention endpoints.

Aim 2: Fidelity

- Therapist adherence to protocol: Average $\leq 75\%$
- Therapist competence in administration: Average < 2
- Participant satisfaction: Average Client Satisfaction Questionnaire score ≤ 16
- Participant engagement: Average Rehabilitation Participation Scale score ≤ 3

Aim 3: Effect

- Average Bangor Goal Setting Interview Goal Attainment change of ≤ 1 with lower 95% CB below 0.

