6.3 MEASURES TO MINIMIZE BIAS: RANDOMIZATION AND BLINDING

Participants will be randomized to treatment arm (MC, Control)* stratified by sex and MoCA score [25/26]⁶⁵. The study statistician created a randomization process that is implemented through REDCap by an independent person ([name]). Immediately after a participant completes Pre assessment, the tester informs [name], via email, of their study ID, sex, and MoCA score (stratification variables). Within 2 days of being informed, [name] will use the REDCap randomizer to assign treatment group and will inform the corresponding therapists, via email, that a participant has been assigned to their group. Only [name] and the statistician can view the randomizer and its results. To maintain PI blinding during therapist supervision, the participants or treatment sessions under discussion will not be identified by study ID.

Personnel collecting Pre, Post and Follow-up data, which includes the study coordinator, will remain blind to treatment arm throughout the entirety of the study. They will not know which therapists are administering which intervention. Inadvertent unblinding of testers will be documented (yes/no, notes). Most of the outcomes, including the primary efficacy outcome (BGSI, Aim 3), are collected via computer, so inadvertent unblinding should not bias the data.

Personnel responsible for rating the audio files for fidelity (Aim 2) will be blind to study purpose. Due to the nature of their work, they will likely come to understand that there are two general intervention approaches being delivered and which therapists are delivering which approach; however, having no knowledge of the study aims and hypotheses and clear criteria for rating should reduce any associated biases in their ratings.

Participants will be aware that they have been randomly assigned to one of two interventions, but they will be given no information on what the other intervention entails, nor will they be informed which is the hypothesized “active” (MC) or Control intervention. In the Follow-up assessment, participants will be asked if they think they received the active or control intervention (yes/no/I don’t know with an option to provide an open-ended response describing why).

*Randomization ratios over the course of the study due to therapist availability:

- November 2019-December 2020 = 2:1, MC:Control
- January 2021- ~2021 = 1:2, MC:Control
- ~July 2021- = 1:1, MC:Control

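### The Aim 2a rows of the Section 9.2 precision table do not match H2a: Proficiency is centred on 3 rather than the benchmark of 2, and n=153 counts Control sessions

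*Combined protocol and SAP*

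**What the plan says.** The Section 9.2 table is captioned "Confidence bounds around target thresholds assuming 15% attrition (for Aim 2"), at a 95% confidence level. Three of its rows matter here.

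- **Proficiency.** The row "Proficiency (n=153 observations") gives 3 (2.9 to 3.1). Section 8.1 defines the rating from 0 to 3, with the top anchor "3=Proficient; averaged for a competence score". H2a (Section 9.1) and the Aim 2 analysis (Section 9.4) set the benchmark at 2 or more out of 3. Section 3 declares failure at "Therapist competence in administration: Average < 2".
- **Adherence.** The row gives 80% (78 to 82), also with n=153. The 80% agrees with H2a. Section 8.1 plans to rate 30% of sessions, n=180, drawn from MC and Control and "evenly distributed across condition, OT, treatment session number, and study month". H2a is a statement about how therapists deliver MC.
- **Aim 1.** The row labelled "Recruitment and retention" gives 85% (73 to 93). H1 sets 85% for retention, and for completion within 12 weeks, in both treatment groups. Its recruitment target is a count, 4 per month. Section 9.4 says the 73% lower bound rests on N=60 and applies it to retention and completion.

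**The concern.** Feasibility and fidelity are the primary aims of this pilot, and this table is where the plan states how precisely 60 participants can address them. Section 9.4 refers back to it. A precision statement is useful only if it is centred on the threshold that will be judged and uses the observations that will enter that judgement.

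The Proficiency row fails the first condition, so a reader cannot set it against the benchmark of 2. Both Aim 2a rows fail the second. Control deliberately leaves out strategy work, metacognition, mediation and action plans (Section 6.1.1), so Control sessions carry no information on how well MC is delivered. Counting them makes the fidelity bounds look tighter than the MC sessions can support.

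The Aim 1 row raises a lesser question: whether H1 is to be judged in each arm or overall.

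**Working it through.** **1. Where 153 comes from.** The inputs are 60 participants, 10 sessions each, 30% rated (Section 8.1) and 15% attrition (Section 9.2).
60 × 10 × 0.30 = 180; 180 × 0.85 = 153. The plan's figure is reproduced exactly, and it includes Control sessions.
MC only: 30 × 10 × 0.30 = 90; 90 × 0.85 = 76.5, or about 76.

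**2. Effect on the half-widths.** For a mean of independent observations, half-width = 1.96 × SD / √n. With the same SD, moving from 153 to 76.5 multiplies it by √(153/76.5) = 1.41.

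**3. Adherence.** The printed half-width is 2 points, so 2 × 1.414 = 2.83 and the interval is 80 ± 2.8 = 77.2 to 82.8. The bounds are printed to whole points, so the true half-width could be 1.5 to 2.5. That gives 1.5 × 1.414 = 2.1 to 2.5 × 1.414 = 3.5. Even at 3.5 the lower bound is 76.5, above the 75% failure line in Section 3.

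**4. Proficiency as printed.** Half-width 0.1 at n=153 implies SD = 0.1 × √153 / 1.96 = 0.63. On a scale capped at 3, a mean of exactly 3 requires every rating to be 3, so SD = 0. The centre and the width are therefore incompatible, and 3.1 lies outside the scale.

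**5. Proficiency at the benchmark.** The centre is 2. If the printed half-width of 0.1 carries over to the MC Fidelity Tool, the MC-only half-width is 0.1 × 1.414 = 0.14. Allowing for rounding (0.05 to 0.15), it is 0.07 to 0.21. The documents give no SD for this tool, so this is conditional.

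**6. Aim 1.** The exact (Clopper–Pearson) 95% interval for x out of n runs from the 0.025 quantile of Beta(x, n−x+1) to the 0.975 quantile of Beta(x+1, n−x).

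| Count | Rate | Exact 95% interval |
|---|---|---|
| 51/60, arms pooled | 85.0% | 73.4 to 92.9 |
| 25/30, one arm | 83.3% | 65.3 to 94.4 |
| 26/30, one arm | 86.7% | 69.3 to 96.2 |

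The first line reproduces the printed 73 to 93. The Wilson (73.9 to 91.9) and Wald (76.0 to 94.0) intervals do not. Since 0.85 × 30 = 25.5, the smallest count that meets 85% in one arm is 26.

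**The case against.** Nothing here is a slip of arithmetic: 153 and 73 to 93 both reproduce. The Adherence target and all three Aim 2b targets (24, 4 and 80%) agree with the hypotheses. Rating Control sessions is legitimate, because Section 9.4 needs them to compare Proficiency between arms. Section 9.2 itself says these calculations were not required for this grant type. All of this stands, and it keeps the point small. None of it explains a Proficiency target of 3, or makes Control sessions relevant to MC delivery.

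Four stronger readings are tempting, and the documents do not support them.

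- A reader might infer that the Proficiency row should simply be reprinted as 1.86 to 2.14. That interval uses an SD taken from the very row that cannot be right. The row cites an outside fidelity study, and the documents do not show that study's scale or SD. Only the centre of 2 is secure.
- A reader might infer that the retention bound is wrong or that the pooling is concealed. Section 9.4 states N=60, and the Section 3 failure criteria, such as the one on "retention in the study intervention", name no arm. H1's reference to both groups can be read per arm or overall. The mismatch is with H1's wording; the figure is correct for what it describes.
- A reader might infer that the study could now miss a failure it would otherwise have declared. The adherence calculation shows no such change, and no other threshold conclusion is shown to move.
- A reader might go on to ask for a different unit of analysis for the t-test or different therapist-level reporting. The mismatch in this table does not establish a need for either.

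**Conclusion.** The inconsistency is real but minor. The Proficiency row is wrong on its face, because the plan's threshold is 2 and 3.1 is unattainable. This needs no assumption.

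For both Aim 2a rows, the relevant number of sessions is about 76 rather than 153, and the half-widths are about 1.4 times those printed. This rests on three assumptions: roughly 1:1 final allocation (Section 6.3 changes the ratio over the course of the study), an even split of rated sessions by arm, and sessions treated as independent. Repeated sessions within participants and therapists would normally widen the bounds further.

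The Aim 1 point is secondary. The pooled bound fits the failure rule and is disclosed, but it is not the bound for H1 if H1 is read by arm. In that case the lower limit is 69% rather than 73%.

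**What to change.** In the Section 9.2 table:

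1. **Proficiency:** set the target to 2, base it on about 76 MC sessions, and recompute the bounds from an SD that applies to the 0–3 MC Fidelity Tool.
2. **Adherence:** base it on about 76 MC sessions and print about 80% (77 to 83), recomputed from the unrounded preliminary SD.
3. **Aim 1:** relabel the row *Retention and completion*. Then choose one of two courses. Either state that H1 is judged on the pooled rate and keep 85% (73 to 93), or print 26/30 per group = 87% (69 to 96) and change the 73% floor in Section 9.4 to 69% in each group.
4. **Note under the table:** say that the Aim 2a bounds treat sessions as independent.

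The cost is three table rows, one note and at most a sentence or two on H1. The stated precision becomes slightly less favourable. No extra participants, ratings or data are needed.
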